12.1 Extent of Exposure

12.1.1 Treatment Administration

Table 12.1.1.1 Number of cycles administered and dose intensity.

No. of cycles administered per patient	N	%
1		
2		
3		
...		
Mean, Standard Deviation, Median (Range)		
Time on treatment* (weeks)		
Median		
Range		
Mean		
Standard Deviation		
PM01183 cumulative dose (mg)		
Median		
Range		
Mean		
Standard Deviation		
PM01183 dose intensity (mg/m ² /wk)		
Median		
Range		
Mean		
Standard Deviation		
PM01183 relative dose intensity (%)		
Median		
Range		
Mean		
Standard Deviation		

Note: Also for s1 and s2; (*) Time on treatment: defined as date of last infusion plus 30 days, or date of death or subsequent therapy (whichever comes first) minus date of first infusion.

12.1.2 Cycle Delays

The first cycle will be excluded from all calculations.

Listing 12.1.2.1 Delays.

Patient id.	CTFI*	Delayed cycle	Delayed cycle start date	Previous cycle	Previous cycle start date	Dose delay calculated. (days)	Reason for dose delay	Dose delay, spec.

(*) Only for SCLC (RR, R, S, VS).

Table 12.1.2.2 Number of patients and cycles with dosing delay, any relationship.

	N	%
No. of patients treated		
No. of patients susceptible of delay		
No. of patients with any dose delay		
No. of cycles administered		
No. of cycles susceptible to be delayed		
No. of cycles with dosing delay		
No. of patients with		
No cycles delayed		
1 cycle delayed		
2 cycles delayed		
≥ 3 cycles delayed		

Note: Also for s1 and s2.

Table 12.1.2.3 Number of patients and cycles with dosing delay, treatment related.

	N	%
No. of patients treated		
No. of patients with drug related dose delay		
No. of cycles administered		
No. of cycles susceptible to be delayed		
No. of cycles with drug related dose delay		
No. of patients with		
No cycles delayed		
1 cycle drug related delayed		
.....		

Note: Also for s1 and s2.

Table 12.1.2.4 Reasons for dosing delay according to the relationship.

Reasons for delays	N	%
No. of patients with any dose delay		
Treatment-related	X	XX.X
Hematological		
Non-hematological		
Both		
Non-treatment-related		
No. of cycles with any dose delay	N	%
Treatment-related	X	XX.X
Hematological		
Non-hematological		
Both		
Non-treatment-related		

Note: Also for s1 and s2;

Table 12.1.2.5 Length of dosing delay.

Length of delay	Median (range)	Treatment-related**		Non-treatment-related		Total	
		N	%	N	%	N	%
Length of delay							
<= 7 days							
>7 days and <=14 days							
> 14 days							

Note: Also for s1 and s2.

Listing 12.1.2.6 Cycle delays due to AEs.

Patient id.	CTFI*	Cycle	Preferred term code	Adverse event reported (verbatim)	Grade	Relationship	Onset date	Resolved date	No. of days with delay	Action taken	Significant consequences

AEs with action = 'Dose delayed' or 'Reduced and delayed'. (*) Only for SCLC (RR, R, S, VS).

12.1.3 Dose Reductions

The first cycle will be excluded from all calculations.

All dose reductions should be considered and described, specifying the reason for reduction (hematological toxicity, non-hematological toxicity or other causes).

Listing 12.1.3.1 Dose reductions.

Patient id.	CTFI*	Cycle	Day	Cycle start date	Previous dose	Reduced dose	Reason for dose reduction	Dose reduction Spec.

(*) Only for SCLC (RR, R, S, VS).

Table 12.1.3.2 Number of patients and cycles with dose reduction, any relationship.

	N	%
No. of patients treated	X	XX.X
No. of patients susceptible to have a dose reduction		
No. of patients with any dose reduced		
No. of patients with:		
No PM01183 reduction		
1 cycle with PM01183 dose reduced		
2 cycles with PM01183 dose reduced		
No. of cycles administered		
No. of cycles susceptible to have any dose reduced		
No. of cycles with PM01183 dose reduced		

Note: Also for s1 and s2.

Table 12.1.3.3 Number of patients and cycles with dose reduction, treatment related.

	N	%
No. of patients treated	X	XX.X
No. of patients with any dose reduced (Treatment-related)		
No. of patients with:		
No PM01183 reduction		
1 cycle with PM01183 dose reduced (Treatment-related)		
2 cycles with PM01183 dose reduced (Treatment-related)		
No. of cycles administered		
No. of cycles susceptible to have any dose reduced		
No. of cycles with PM01183 dose reduced (Treatment-related)		

Note: Also for s1 and s2.

Table 12.1.3.4 Number of patients and cycles with dose reduction according to the relationship.

Reasons for reductions	N	%
No. patients with reductions		
Treatment-related	X	XX.X
Hematological		
Non-hematological		
Both		
Non-treatment-related		
No. of cycles patients with reductions	N	%
Treatment-related	X	XX.X
Hematological		
Non-hematological		
Both		
Non-treatment-related		

Note: Also for s1 and s2.

Listing 12.1.3.5 Dose reductions due to AEs.

Patient id.	CTFI*	Total no. of cycles	Cycle	Preferred term code	Adverse event reported (verbatim)	Grade	Relationship	Onset date	Resolution date	Action taken	Significant consequences

AEs with action = 'Dose reduced/adjusted' or 'Reduced and delayed'. (*) Only for SCLC (RR, R, S, VS).

12.1.4 Temporarily Interrupted Infusions

A listing of the patients who had temporarily interrupted infusions, with the corresponding reasons, will be provided.

Listing 12.1.4.1 Interrupted infusions.

Patient id.	Cycle	Reason

12.1.5 Prophylactic Medication Administration

A listing of the patients who have not received corticosteroids, 5-HT3 antagonists, prokinetics and other antiemetics or equivalents with the corresponding reasons will be reported.

Listing 12.1.5.1 Patients and cycles with prophylactic medication not taken per protocol.

Patient id.	Cycle	Prophylactic medication not taken*	Reason
...			

(*) Corticosteroids, 5-HT3 antagonists, prokinetics and other antiemetics.

12.2 Adverse Events

12.2.1 Treatment Emergent Adverse Events

Treatment emergent adverse events will be described in this section; treatment-related events (stated as related to the study drug or of unknown relationship) will be tabulated.

Type of toxicity and worst grade or severity by cycle and by patient will be summarized according to the Preferred Term coded with MedDRA. Tables will be organized per category of events using System Organ Class of MedDRA.

Each table, listing and figure displayed in this section will have a comprehensive header identifying the tumor type (cohort) and the total population (if applicable).

12.2.2 Display of Treatment Emergent Adverse Events

Table 12.2.2.1 Summary of treatment emergent adverse events per patient.

Category**	N	%
Patients with at least one TEAE regardless of relationship		
Any treatment-related** AE		
Any grade ≥3 TEAE		
Any treatment-related grade ≥3 AE		
Any Treatment emergent SAE in DB		
Any treatment-related SAE		
Any grade ≥3 Treatment emergent SAE		
Any treatment-related grade ≥3 SAE		
TEAEs leading to death		
Treatment-related AE leading to death		
TEAEs leading to dose delay***		
TEAEs leading to dose reduction***		
TEAEs leading to treatment discontinuation		
Treatment-related AEs leading to treatment discontinuation		

Note: Also for s1 and s2; (*) Percentage based on number of treated patients; (**) Treatment related adverse event is every event whose relationship is 'Yes' or 'Unknown'. (***) TEAEs leading to dose delay and reduction according to the AE form, with no delay or reduction because the patient discontinues treatment and there is no additional cycle administered are not counted here.

Table 12.2.2.2 Treatment-related adverse events. Worst grade by patient.

Table 12.2.2.3 Treatment-related adverse events. Worst grade by cycle.

Table 12.2.2.4 Treatment emergent adverse events regardless of relationship. Worst grade by patient.

Table 12.2.2.5 Treatment emergent adverse events regardless of relationship. Worst grade by cycle.

Tables 12.2.2.2 to 12.2.2.5 will have the following pattern, but depending on the number and severity of the adverse events observed, the NCI-CTCAE v4 grades may be grouped as ≥1 and ≥3 categories.

SOC	Preferred term	Grade 1		...	Grade 4		Grade ≥1		Grade ≥3
		N	%		N	%	N	%	
Blood and lymphatic system disorders	Anemia NOS			...					
	...								
	...								
Cardiac disorders	Arrhythmia NOS								
	...								

Note: Tables 12.2.2.2 and 12.2.2.4 also for s1 and s2.

Listing 12.2.2.6 Treatment-related grade ≥3 adverse events. Worst grade per patient.

Listing 12.2.2.7 Treatment-related grade ≥3 adverse events. Worst grade by cycle.

Listing 12.2.2.8 Grade ≥3 treatment emergent adverse events regardless of relationship. Worst grade per patient.

Listing 12.2.2.9 Grade ≥3 treatment emergent adverse events regardless of relationship. Worst grade by cycle.

Listings 12.2.2.6 to 12.2.2.9 will have the following pattern:

Patient id.	CTFI**	Cycle*	SOC name	Preferred term	Grade

(*) NA in the per patient summaries; (**) CTFI only for SCLC patients (RR, R, S, VS).

At the time of the analysis, if appropriate, grouping of similar or clinically related AEs will be made.

12.3 Serious Adverse Events and Deaths.

Each table, listing and figure displayed in this section will have a comprehensive header identifying the tumor type (cohort) or the total population (if applicable).

12.3.1 Serious Adverse Events

Listing 12.3.1.1 SAEs.

Patient id.	Preferred term code	Onset cycle	Intended Dose of onset cycle (mg/m2)	Adverse event reported (verbatim)	Status	Grade	Relationship	Onset date	Resolution date	Action	Serious criteria

The Pharmacovigilance Department will provide the narratives of the SAEs from the Pharmacovigilance Database (DB).

Table 12.3.1.2 Treatment-related serious adverse events. Worst grade by patient.

Table 12.3.1.3 Treatment-related serious adverse events. Worst grade by cycle.

Table 12.3.1.4 Serious adverse events regardless of relationship. Worst grade by patient.

Table 12.3.1.5 Serious adverse events regardless of relationship. Worst grade by cycle.

Tables 12.3.1.2 to 12.3.1.5 will have the following pattern, but depending on the number and severity of the adverse events observed, the NCI-CTCAE v4 grades may be grouped as ≥ 1 and ≥ 3 categories.

SOC	Preferred term	Grade 1			...	Grade 4		Grade ≥ 1		Grade ≥ 3	
		N	%	...		N	%	N	%	N	%
Blood and lymphatic system disorders	Anemia NOS										
	...										
	...										
Cardiac disorders	Arrhythmia NOS										
	...										

Note: Tables 12.3.1.2 and 12.3.1.4 also for s1 and s2;

Listing 12.3.1.6 Treatment-related grade ≥ 3 serious adverse events. Worst grade per patient.

Listing 12.3.1.7 Treatment-related grade ≥ 3 serious adverse events. Worst grade by cycle.

Listing 12.3.1.8 Grade ≥ 3 serious adverse events regardless of relationship. Worst grade per patient.

Listing 12.3.1.9 Grade ≥ 3 serious adverse events regardless of relationship. Worst grade by cycle.

Listings 12.3.1.6 to 12.3.1.9 will have the following pattern:

Patient id.	CTFI**	Cycle*	SOC name	Preferred term	Grade

(*NA in the patient summaries; (**) CTFI only for SCLC patients (RR, R, S, VS).

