7.7.2 Reporting Serious Adverse Events

The Sponsor will collect SAEs from the time of signing of the informed consent form (ICF) until 30 days after administration of the last dose of study drug(s)/IMP(s) or until the start of a new antitumor therapy, whichever occurs first. Beyond this period of time, only those SAEs suspected to be related to the IMP will be collected. Nonetheless, the Sponsor will evaluate any safety information that is spontaneously reported by an Investigator beyond the time frame specified in the protocol.

All SAEs (as defined above) regardless of relationship to the study drug(s)/IMP(s) must be reported immediately and always within 24 hours to the Pharma Mar S.A. Pharmacovigilance Department as appropriate: electronically (e-CRF), fax ([contact]), e-mail ([contact]) or telephone ([contact]). Out of office hours [Greenwich Meridian Time (GMT)], assistance on SAE reporting can be obtained by calling the Pharmacovigilance Department at [contact]. SAEs initially reported by phone must be followed by a completed electronic SAE reporting on e-CRF from the investigational staff within one working day.

If the SAE occurs after the patient's registration has been confirmed, this information will preferably be reported electronically by completing the applicable eCRF sections.

Those SAEs occurring during the screening phase (from ICF signature to registration) and after off-study will be reported using a paper "SAE form" that must be forwarded as mentioned above and always within 24 hours to the Pharmacovigilance Department.

All SAEs suspected to be related to the IMP(s) must be followed until the event or its sequelae resolves or stabilizes at an acceptable level by the Investigator and the clinical monitor or his/her designated representative.

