7.1 Toxicity and Adverse Events

All the adverse events will be coded using the Medical Dictionary for Regulatory Activities (MedDRA).

The toxicity evaluation will be coded with the National Cancer Institute Common Terminology Criteria for Adverse Events (NCI-CTCAE) v4.

Treatment-emergent adverse events (TEAE) are defined as any adverse events aggravated in severity from baseline or having their onset between the first dose of the study drug and 30 days after the last treatment dose, death or date of further therapy (whichever comes first). Adverse Events Related to Study Drug or with Unknown relationship occurring more than 30 days after the last dose will also be taken into account as TEAEs.

Summary of overall AEs will be done by System Organ Class (SOC) and Preferred Term (PT), by severity (worst toxicity grade), by relationship to the study drug and by AE outcome. Tables will be

organized by category of events using SOC (i.e. alphabetical order) and PT in descending frequencies (i.e., from higher to lower).

A frequency table or listing will be made for the AEs leading to cycle delay, dose reduction or withdrawal of study medication. Adverse events with outcome of death will also be presented by relationship to the study drugs.

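### The SAE outputs regardless of causality (SAP Tables 12.3.1.4–12.3.1.5, Listings 12.3.1.8–12.3.1.9) are not limited to treatment-emergent events, although SAEs are collected from consent and the matching rows of Table 12.2.2.1 are so limited

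*SAP*

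**What the plan says.** SAP 7.1 counts an adverse event as treatment-emergent if it worsened from baseline or is one "having their onset between the first dose of the study drug and 30 days after the last treatment dose" (or death or further therapy, if sooner). Later events that are drug-related or of unknown relationship are added.

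SAP 12.2 uses that definition. One of its tables is titled "Table 12.2.2.4 Treatment emergent adverse events regardless of relationship. Worst grade by patient", and the summary Table 12.2.2.1 has the rows "Any Treatment emergent SAE in DB" and "Any grade ≥3 Treatment emergent SAE".

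SAP 12.3.1 then plans "Table 12.3.1.4 Serious adverse events regardless of relationship. Worst grade by patient" and "Table 12.3.1.5 Serious adverse events regardless of relationship. Worst grade by cycle", with Listings 12.3.1.8 and 12.3.1.9 as the grade ≥3 equivalents. The treatment-emergent label is absent from all four titles.

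On collection, Protocol 7.7.2 states: "The Sponsor will collect SAEs from the time of signing of the informed consent form (ICF) until 30 days after administration of the last dose". The screening table in Protocol 5.4 makes SAEs the one class of event that must be recorded before treatment starts. The safety set is all treated patients (SAP 4.3 and the opening of SAP 12).

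**The concern.** Two outputs in the same safety section describe SAEs irrespective of causality under different time windows. A programmer following the titles would apply the treatment-emergent filter in 12.2 and in the cause-of-death table of 12.3.2, whose rows are labelled TEAE, but not in 12.3.1. An event that happened before any drug was given could then appear in the SOC and preferred-term SAE profile.

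The trial has no control arm, so these tables stand alone as the detailed SAE profile. Table 12.3.1.4 is also to be repeated for the resistant and sensitive SCLC subsets, where denominators are smaller.

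**Working it through.** The plan states no figure on this point, so there is none to reproduce. The check compares the texts and then gives a size per event.

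**1. Is a time limit supplied elsewhere?**
- SAP 7.4 says only that deaths and other SAEs are to be tabulated.
- The introductions to SAP 12 and 12.3 fix the population and the table headers, not a time window.
- The treatment-emergent statement in SAP 12.2.1 covers its own section only.
- No limit is supplied.

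**2. Can a pre-dose SAE be in the data for a treated patient?**
- Collection starts at consent (Protocol 7.7.2).
- SAEs after registration go preferably into the eCRF; those between consent and registration go on a paper form to Pharmacovigilance (Protocol 7.7.2).
- Registration is assumed to be the day before Cycle 1 Day 1, but the schedule of assessments provides for a longer gap.
- SAP Listing 14.1.21 covers baseline adverse events and has an SAE column.
- So it can, at least for the interval from registration to first infusion.

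**3. Where would such an event be counted?** Take an SAE with onset after registration and before first infusion, in a patient who is then treated, that does not worsen on drug.
- SAP 7.1 definition: not met.
- Table 12.2.2.1, treatment-emergent SAE row: not counted.
- Table 12.3.1.4 as titled: counted under its SOC and preferred term.
- Listing 12.3.1.8 as titled: listed if grade ≥3, while the grade ≥3 treatment-emergent SAE row omits it.
- Table 12.3.1.5 and Listing 12.3.1.9: no treatment cycle to assign. SAP 7 maps end-of-treatment visits to the last cycle but gives no rule for pre-dose events.

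**4. Does the late end of the window also differ?** No. After 30 days or new therapy the protocol collects only SAEs suspected to be drug-related, and SAP 7.1 counts late related events as treatment-emergent. The mismatch is at the front end only.

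**5. Size per event.** Let k be the number of treated patients whose only SAE was before dosing, and N the treated patients in the cohort. The share with an SAE under the Table 12.3.1.4 definition rises by 100 × k/N points; the Table 12.2.2.1 row does not move. The documents give no k, so 0 to 3 is assumed. N is taken as the planned 25, 50 and 100; these are evaluable-patient targets, and more patients treated would make the effect slightly smaller.
- N=25: 1/25 = 4 points per patient; 0 to 12 points for k = 0 to 3.
- N=50: 1/50 = 2 points per patient; 0 to 6 points.
- N=100: 1/100 = 1 point per patient; 0 to 3 points.

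**The case against.** The strongest reply is that the SAP nowhere instructs anyone to put pre-dose SAEs into 12.3.1. Section 12 is the on-drug safety section, and baseline adverse events have their own place in SAP 8.3 and 11.1.19. The by-cycle outputs presuppose a cycle, so a pre-dose event might simply fall out of them. SAP 8.15 refers to a separate conventions document that could hold the filter. Never-treated patients are excluded, and SAEs reported on paper before registration may not reach the clinical database. No efficacy result or stopping rule is touched; the safety stopping rules use treatment-related deaths.

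Much of this bears on size, and there it stands. It does not remove the gap. The baseline tables in 11.1.19 do not single out serious events, and nothing says that an event shown there is left out of 12.3.1. A possible filter in an unseen document is not a definition in the SAP. The neighbouring sections state the limit explicitly, so its absence here reads as an omission: according to SAP 15.2, the revision that relabelled the 12.2 outputs and the cause-of-death rows also introduced these SAE tables without the label.

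**Conclusion.** The point holds as an inconsistency of definition. Two tables and two listings do not follow the SAP's own treatment-emergent definition, while the summary rows they should support do. The numbers differ only if at least one treated patient has a pre-dose SAE that does not worsen on drug. The documents do not say how many such patients there are, and the effect is probably small.

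Four stronger readings are tempting and are not supported:

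- **The report would carry two conflicting totals for patients with any SAE.** The shell for Table 12.3.1.4 has SOC and preferred-term rows and no any-SAE total, so the discrepancy lies in definition and in term-level counts.
- **The outputs could not be reconciled.** Listings 12.3.1.1, 14.1.21 and 16.2.7 show onset dates, and Listing 16.2.1 shows the first infusion date, so a pre-dose SAE can be identified.
- **A sizeable share of SAEs would be pre-dose.** With an equal daily SAE rate, 7 to 14 screening days and 60 to 120 treatment days, the share would be 7/(7+120) = 5.5% to 14/(14+60) = 18.9%. Neither the durations nor the equal rate comes from the documents, and the sum ignores the paper-form route. Counting only one day from registration to infusion, the same formula gives 1/(1+120) = 0.8% to 1/(1+60) = 1.6%.
- **All the SAE tables are affected.** An SAE before any drug should not be attributed to the drug, and the treatment-related rows of Table 12.2.2.1 are not labelled treatment-emergent either. Tables 12.3.1.2–12.3.1.3 and Listings 12.3.1.6–12.3.1.7 therefore match their counterparts.

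**What to change.** Define and title Tables 12.3.1.4 and 12.3.1.5 and Listings 12.3.1.8 and 12.3.1.9 as treatment-emergent SAEs per SAP 7.1. Show SAEs with onset from consent to first infusion in a separate short listing, or with the baseline adverse events in SAP 11.1.19. Leave the treatment-related Tables 12.3.1.2–12.3.1.3 and Listings 12.3.1.6–12.3.1.7 as they are. Listing 12.3.1.1 can keep all SAEs, since it already shows the onset date.

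The cost is one filter and one short listing, with no new data.

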12.3.2 Deaths

Table 12.3.2.1 Cause of death.

Reason*	N	%
Malignant disease		
Study drug-related TEAE		
Non-study drug-related TEAE		
Other		
Total		

Note: Also for s1 and s2; (*) Denominator=Number of patients who died.

Listing 12.3.2.2 Deaths.

Patient id.	CTFI***	Death date	Cause	No. of cycles administered	Last infusion date	Time on treatment*	Time from Last dose**	Comments	Autopsy

(*) Time on treatment: defined as date of last infusion plus 30 days, or date of death or subsequent therapy (whichever comes first) minus date of first infusion. (**) Time from last dose defined as date of death minus date of last infusion. (***) Only for SCLC cohort (RR, R, S, VS).

Listing 12.3.2.3 Adverse events with outcome of death.

Patient id.	Cycle	Preferred term code	Adverse event reported (verbatim)	Grade	Relationship	Onset date	Date of death	Action

12.4 Clinical Laboratory Evaluation

Each table, listing and figure displayed in this section will have a comprehensive header identifying the tumor type (cohort) or the total population (if applicable).

12.4.1 Hematological Abnormalities during Treatment

Hematological toxicities classified according to the NCI-CTCAE will be calculated for all cycles. The worst grade reached by each patient during treatment will also be calculated.

Table 12.4.1.1 Hematological abnormalities, worst grade per patient.

Table 12.4.1.2 Hematological abnormalities, worst grade per cycle.

Tables 12.4.1.1 and 12.4.1.2 will have the following pattern but depending on the number and severity of the adverse events observed, the NCI-CTCAE v4 grades may be grouped as ≥ 1 and ≥ 3 categories.

	Grade 1		...	Grade 4		Grade ≥ 1		Grade ≥ 3	
	N	%		N	%	N	%	N	%
Anemia									
Leukopenia									
Neutropenia									
Lymphopenia									
Thrombocytopenia									

Note: Tables 12.4.1.1 and 12.4.1.2 also for s1 and s2.

Listing 12.4.1.3 Grade ≥ 3 hematological abnormalities. Worst grade per patient.

Patient id.	Test	Grade

Listing 12.4.1.4 Grade ≥ 3 hematological abnormalities. Worst grade per cycle.

Patient id.	Cycle	Test	Grade

Listing 12.4.1.5 Hematological tests not assessed by patient and cycle.

Patient id.	Total number of cycles	Cycle with missing lab. test	Lab. test

